5.2 Study Materials

The following materials will be provided at study start:

- NCI CTCAE version 4.0
- BMS-936558 (nivolumab) Investigational Brochure
- Pharmacy Binder
- Laboratory manuals for collection and handling of blood [REDACTED] and tissue specimens
- Site manual for operation of interactive voice response system (for study enrollment)
- Serious Adverse Event (or eSAE) case report forms
- Pregnancy Surveillance Forms
- RECIST 1.1 pocket guide
- PRO manual

Each site will be provided with PRO questionnaires. Subjects will complete these at the time of the scheduled visits, prior to any study procedures and study drug infusion. During the survival follow-up period beyond X02, the EQ-5D PRO will be administered at a frequency of every 3 months for the first 12 months, then every 6 months thereafter, as permitted by local law. (see schedule [Table 5.1-2](#) and [Table 5.1-3](#) for frequency of assessments).

5.3 Safety Assessments

5.3.1 Screening Assessments

Screening assessments and procedures must be completed in accordance with [Table 5.1-1](#).

5.3.2 On-Study Safety Assessments and Procedures

The following assessments will be monitored as specified in Table 5.1-2 starting on Cycle 1 Day 1 (C1D1) and will continue at the specified frequency until discontinuation from the study.

- Vital signs including temperature, blood pressure, heart rate, respiratory rate, oxygen saturation by pulse oximetry at rest (also monitor amount of supplemental oxygen if applicable) within 72 hours prior to dosing. Obtain prior to dosing and at any time a subject has any new or worsening respiratory symptoms. If a subject shows changes in oxygen saturation or supplemental oxygen requirement, or other pulmonary-related signs (hypoxia, fever) or symptoms (eg. dyspnea, cough) consistent with possible pulmonary adverse events, the subject should be immediately evaluated to rule out pulmonary toxicity, according to the Investigator's Brochure and in [Appendix 2](#) for the suspected pulmonary toxicity management algorithm.

Concomitant medications taken throughout the study duration should be recorded within the eCRF.

[REDACTED]

For subjects who discontinue study treatment due to toxicity, please follow the procedures for the last scheduled visit on study treatment (prior to discontinuation of study therapy and follow-up visits) from either [Table 5.1-2](#) or [Table 5.1-3](#) [REDACTED]

5.3.3 Follow-up and Survival Procedures

Subjects will be monitored for safety according to Table 5.1-2 and Table 5.1-3.

5.3.4 Imaging Assessment for the Study

Any incidental findings of potential clinical relevance that are not directly associated with the objectives of the protocol should be evaluated and handled by the Study Investigator as per standard medical/clinical judgment.

5.4 Efficacy Assessments

5.4.1 Screening (Baseline visit) and On-Study Efficacy Assessments

Study evaluations will take place in accordance with [Table 5.1-1](#) and Table 5.1-2, according to RECIST 1.1 criteria.⁵⁴ High resolution CT with oral/intravenous contrast or contrast-enhanced MRI is the preferred imaging modalities for assessing radiographic tumor response. If a subject has a known allergy to contrast material, please use local prophylaxis standards to obtain the assessment with contrast if at all possible, or use the alternate modality. In cases where contrast is strictly contraindicated, a non-contrast scan will suffice. Screening assessments should be performed within 28 days of start of study treatment. Brain MRI is the preferred imaging method for evaluating CNS metastasis, and assessment is required during screening in subjects with a known history of treated brain metastases. All known or suspected sites of disease (including CNS) should be assessed at screening and at subsequent assessments using the same imaging method and technique. If more than one method is used at screening, then the most accurate method according to RECIST 1.1 should be used when recording data, and should again be used for all subsequent assessments. Bone scan, PET scan, or ultrasound are not adequate for assessment of RECIST response. In selected circumstances where such modalities are the sole modality used to assess certain non-target organs, those non-target organs may be evaluated less frequently. For example, bone scans may need to be repeated only when complete response is identified in target disease or when progression in bone is suspected. Previously treated CNS metastases are not considered measurable lesions for purposes of RECIST determined response. Subjects with a history of brain metastasis should have surveillance MRI approximately every 12 weeks, or sooner if clinically indicated. After 24 months of treatment, the frequency of surveillance brain MRI procedures will be every 6 months or earlier, if clinically indicated for patients with brain metastases.

Radiographic tumor assessments will be conducted at Week 9 (\pm 5 days) and every 8 weeks (\pm 5 days) thereafter through 24 months of treatment, disease progression (or until discontinuation of study therapy in patients receiving nivolumab beyond progression), lost to follow-up, or withdrawal of study consent. After 24 months of treatment, tumor assessments will take place regularly every 12 weeks (\pm 5 days) until the end of treatment, disease progression (or

[figure not shown]
until discontinuation of study therapy in patients receiving nivolumab beyond progression), lost to follow-up, or withdrawal of study consent. Tumor assessments for all subjects should continue as per protocol even if dosing is interrupted. Tumor measurements should be made by the same investigator or radiologist for each assessment whenever possible. Changes in tumor measurements and tumor responses to guide ongoing study treatment decisions will be assessed by the investigator using RECIST 1.1 (see [Appendix 1](#) for details of RECIST 1.1).

[figure not shown]
5.4.2 Follow-up and Survival Procedures

[figure not shown]
Subjects who discontinue study treatment prior to progression, and subjects being treated beyond disease progression, will be followed with radiographic tumor assessments every 8 weeks (\pm 5 days) until 24 months of treatment, documented or further disease progression, withdrawal of study consent, or subjects are lost to follow-up. After 24 months of treatment in these subjects, radiographic tumor assessments will be every 12 weeks (\pm 5 days) until documented or further disease progression, withdrawal of study consent, or lost to follow-up.

Radiographic assessments should be performed according to [Section 5.4.1](#).

Survival will be followed after progression, either by direct contact (office visits) or via telephone contact, according to [Table 5.1-3](#) until death, withdrawal of study consent, or lost to follow-up for five years following start of therapy.

5.7 Outcomes Research Assessments

Patient reported outcomes (PRO) will be measured according to Table 5.1-2 and Table 5.1-3, using the following two validated subject self-reported questionnaires: Lung Cancer Symptom Scale (LCSS), and EuroQOL Group's EQ-5D.

Subjects will be asked to complete questionnaires before any clinical activities are performed during visits to the study clinics at on-study visits, and at the designated study visits in the follow-up (post-treatment) phase of the study.

Questionnaires will be provided in the subject's preferred language.

5.8 Other Assessments

Not applicable.

5.9 Results of Central Assessments

Not applicable

6 ADVERSE EVENTS

An **Adverse Event (AE)** is defined as any new untoward medical occurrence or worsening of a preexisting medical condition in a clinical investigation subject administered an investigational (medicinal) product and that does not necessarily have a causal relationship with this treatment. An AE can therefore be any unfavorable and unintended sign (such as an abnormal laboratory finding), symptom, or disease temporally associated with the use of investigational product, whether or not considered related to the investigational product.

The causal relationship to study drug is determined by a physician and should be used to assess all adverse events (AE). The causal relationship can be one of the following:

Related: There is a reasonable causal relationship between study drug administration and the AE.

Not related: There is not a reasonable causal relationship between study drug administration and the AE.

The term "reasonable causal relationship" means there is evidence to suggest a causal relationship.

Adverse events can be spontaneously reported or elicited during open-ended questioning, examination, or evaluation of a subject. (In order to prevent reporting bias, subjects should not be questioned regarding the specific occurrence of one or more AEs.)

6.1 Serious Adverse Events

A **Serious Adverse Event (SAE)** is any untoward medical occurrence that at any dose:

- results in death
- is life-threatening (defined as an event in which the subject was at risk of death at the time of the event; it does not refer to an event which hypothetically might have caused death if it were more severe)
- requires inpatient hospitalization or causes prolongation of existing hospitalization (see **NOTE** below)
- results in persistent or significant disability/incapacity
- is a congenital anomaly/birth defect
- is an important medical event (defined as a medical event(s) that may not be immediately life-threatening or result in death or hospitalization but, based upon appropriate medical and scientific judgment, may jeopardize the subject or may require intervention [eg, medical, surgical] to prevent one of the other serious outcomes listed in the definition above.) Examples of such events include, but are not limited to, intensive treatment in an emergency room or at home for allergic bronchospasm; blood dyscrasias or convulsions that do not result in hospitalization.) Potential drug induced liver injury (DILI) is also considered an important medical event. (See [Section 6.6](#) for the definition of potential DILI.)

Suspected transmission of an infectious agent (eg, pathogenic or nonpathogenic) via the study drug is an SAE.

Although pregnancy, overdose, cancer, and potential drug induced liver injury (DILI) are not always serious by regulatory definition, these events must be handled as SAEs. (See Section 6.1.1 for reporting pregnancies).

NOTE:

The following hospitalizations are not considered SAEs in BMS clinical studies:

- a visit to the emergency room or other hospital department < 24 hours, that does not result in admission (unless considered an important medical or life-threatening event)
- elective surgery, planned prior to signing consent
- admissions as per protocol for a planned medical/surgical procedure
- routine health assessment requiring admission for baseline/trending of health status (eg, routine colonoscopy)
- medical/surgical admission other than to remedy ill health and planned prior to entry into the study. Appropriate documentation is required in these cases
- admission encountered for another life circumstance that carries no bearing on health status and requires no medical/surgical intervention (eg, lack of housing, economic inadequacy, caregiver respite, family circumstances, administrative reason).

6.1.1 *Serious Adverse Event Collection and Reporting*

Following the subject's written consent to participate in the study, all SAEs, whether related or not related to study drug, must be collected, including those thought to be associated with protocol-specified procedures. All SAEs must be collected that occur during the screening period and within 100 days of discontinuation of dosing. If applicable, SAEs must be collected that relate to any later protocol-specified procedure (eg, a follow-up skin biopsy).

The investigator should report any SAE that occurs after these time periods and that is believed to be related to study drug or protocol-specified procedure.

An SAE report should be completed for any event where doubt exists regarding its seriousness.

If the investigator believes that an SAE is not related to study drug, but is potentially related to the conditions of the study (such as withdrawal of previous therapy or a complication of a study procedure), the relationship should be specified in the narrative section of the SAE Report Form.

SAEs, whether related or not related to study drug, and pregnancies must be reported to BMS (or designee) within 24 hours. SAEs must be recorded on the SAE Report Form; pregnancies on a Pregnancy Surveillance Form (electronic or paper forms). When using paper forms, the reports are to be transmitted via email or confirmed facsimile (fax) transmission to:

SAE Email Address: Refer to Contact Information list.

SAE Facsimile Number: Refer to Contact Information list.

For studies capturing SAEs through electronic data capture (EDC), electronic submission is the required method for reporting. The paper forms should be used and submitted immediately, only

in the event the electronic system is unavailable for transmission. When paper forms are used, the original paper forms are to remain on site.

SAE Telephone Contact (required for SAE and pregnancy reporting): Refer to Contact Information list.

If only limited information is initially available, follow-up reports are required. (Note: Follow-up SAE reports should include the same investigator term(s) initially reported.)

If an ongoing SAE changes in its intensity or relationship to study drug or if new information becomes available, a follow-up SAE report should be sent within 24 hours to the BMS (or designee) using the same procedure used for transmitting the initial SAE report.

All SAEs should be followed to resolution or stabilization.

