3 INVESTIGATIONAL PLAN

3.1 Study Design and Duration

In this safety study of nivolumab monotherapy, subjects will undergo screening evaluations to determine eligibility within 28 days prior to first dose. Eligible subjects will be treated with nivolumab administered intravenously over 30 minutes at 3 mg/kg every two weeks. Each

14 day dosing period will constitute a cycle. After 1 year (52 weeks) of treatment all subjects who are still on treatment will be randomized (1:1) to one of the two cohorts, Cohort A or Cohort B.

- Cohort A: Subjects randomized to Cohort A will continue to receive treatment until disease progression, unacceptable toxicity, or withdrawal of informed consent.
- Cohort B: Subjects randomized to Cohort B will discontinue treatment at 1 year (52 weeks). After randomization, subjects will remain on the study and will follow all study assessments [REDACTED]. Upon progression, subjects can receive retreatment.

Subjects who are retreated can continue to receive study drug until further progression, unacceptable toxicity, or withdrawal of informed consent.

Study treatment can continue beyond initial investigator assessed progression, as specified in criteria presented in [Section 4.3.4 Treatment Beyond Disease Progression](#). The study will close after the last enrolled subject completes 5 year follow up.

The study will enroll subjects into 4 subgroups as detailed in [Table 3.1-1](#).

Enrollment will open first to subgroup 1 only. A decision to open enrollment for each of the other subgroups 2-4 will be dependent upon the sponsor review of data from the ongoing Phase 2 and 3 studies for each patient population. The decision will take into account the overall risk/benefit profile for each patient population and the determination will be made whether or not to collect additional safety and efficacy data to supplement that already collected.

At the time of Protocol Amendment 01 (June 2014), all subgroups were opened.

Protocol Amendment 03 (November 2014) allowed for continued enrollment beyond 780 subjects in two of the study subgroups. However, as of Protocol Amendment 04 (December 2014), enrollment under Amendment 03 will stop, but enrollment will continue until 500 additional subjects are treated. Enrollment will continue until a total of 1280 subjects are treated.

[REDACTED]

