3.5 Discontinuation of Subjects from Treatment

Subjects MUST discontinue investigational product (and non-investigational product at the discretion of the investigator) for any of the following reasons:

- Subject's request to stop study treatment
- Any clinical adverse event (AE), laboratory abnormality or intercurrent illness which, in the opinion of the investigator, indicates that continued participation in the study is not in the best interest of the subject
- Pregnancy
- Termination of the study by Bristol-Myers Squibb (BMS)
- Loss of ability to freely provide consent through imprisonment or involuntarily incarceration for treatment of either a psychiatric or physical (eg, infectious disease) illness
- After randomization in Cohort B, until disease progression when subjects are eligible for retreatment
- Other protocol specific reasons for discontinuation as specified in [Section 4.3.5](#).

All subjects who discontinue investigational product should comply with protocol specified follow-up procedures as outlined in [Section 5](#). Subjects in Cohort B continue with the on-study visit schedule ([Table 5.1-2](#)) until disease progression following retreatment or upon a decision to not receive retreatment, unacceptable toxicity, or withdrawal of informed consent. The only exception to this requirement is when a subject withdraws consent for all study procedures including post-treatment study follow-up or loses the ability to consent freely (ie, is imprisoned or involuntarily incarcerated for the treatment of either a psychiatric or physical illness).

If study treatment is discontinued prior to the subject's completion of the study, the reason for the discontinuation must be documented in the subject's medical records and entered on the appropriate case report form (CRF) page.

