Radiographic Tumor Assessment (Chest, Abdomen, Head)	X	Within 28 days prior to first dose. CT/MRI of brain (with contrast, unless contraindicated) required for subjects who have known history of brain metastases or if clinically indicated.. Additional sites of known or suspected disease (including pelvis) should be imaged at the screening visit.
Archived Tumor Tissue or Recent Tumor Biopsy	X	
One formalin-fixed paraffin embedded tumor tissue block, or 10 minimum FFPE unstained slides are to be submitted if available. Submit a copy of the original pathology report along with the sample. Tissue samples from different biopsy procedures are to be submitted if available with each matching pathology report and biopsy date.
 
NOTE: For subjects previously enrolled in CA 209118, tumor tissue and/or laboratory data generated from tissue collected in CA209118 is to be utilized for this study.

Table 5.1-2: On-Study Procedural Outline (CA209153)

Procedure	C1D1 (Cycle 1 Day 1)	Each Cycle (Every 2 weeks) on Day 1	Every 3 Cycles (Every 6 weeks) on Day 1	Every 4 Cycles (Every 8 weeks) on Day 1	Notes
Safety Assessments					
Vital Signs and oxygen saturation ^a	X	X			Within 72 hours prior to dosing. Include temperature, blood pressure, heart rate, respiratory rate, oxygen saturation by pulse oximetry at rest prior to dosing and at any time there are new or worsening respiratory symptoms. (see Section 5.3.2) Patients randomized to Cohort B will be assessed every 2 or 4 weeks for clinical assessment and physical examination per investigator decision. If nivolumab is restarted, every two week assessment schedule must be resumed.
Adverse Events Assessment			Continuously		Continuously assessed using NCI CTCAE v. 4.0.
Physical measurements and target physical exam (including Performance Status)	X	X			Includes weight, ECOG status, and targeted physical exam as clinically indicated Patients randomized to Cohort B will be assessed every 2 or 4 weeks for clinical assessment and physical examination per investigator decision. If nivolumab is restarted, every two week assessment schedule must be resumed.
Laboratory Tests^b					Cohort B: For subjects randomized to Cohort B, lab tests will be performed every 4 weeks. If nivolumab is restarted, every two week lab assessment schedule must be resumed.

Table 5.1-2: On-Study Procedural Outline (CA209153)

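### The 100-day SAE collection rule conflicts with the Cohort B visit schedule, so late SAEs not judged related may be recorded less completely in Cohort B off drug than in Cohort A

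*Combined protocol and SAP*

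**What the plan says.** **Collection rule.** Section 6.1.1 sets the all-cause window: "All SAEs must be collected that occur during the screening period and within 100 days of discontinuation of dosing". After that, "The investigator should report any SAE that occurs after these time periods and that is believed to be related to study drug" or to a protocol procedure. The section has no provision for Cohort B.

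**Dosing.** Sections 3.1 and 4.1 stop Cohort B at 52 weeks, with ± 2 weeks in Table 5.1-2. Section 3.5 lists assignment to Cohort B among the reasons for which product must be discontinued, until progression makes retreatment possible. For Cohort A, Section 3.1 says: "Subjects randomized to Cohort A will continue to receive treatment until disease progression, unacceptable toxicity, or withdrawal of informed consent".

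**Cohort B schedule.** Section 3.5 says "Subjects in Cohort B continue with the on-study visit schedule" of Table 5.1-2, "until disease progression following retreatment or upon a decision to not receive retreatment", unacceptable toxicity or withdrawal of consent. In that table the adverse event row reads "Continuously assessed using NCI CTCAE v. 4.0", with no cohort exception. Section 5.3.2 says the on-study safety assessments "will continue at the specified frequency until discontinuation from the study", that is, not until the end of dosing. Table 5.1-3 starts Cohort B's first follow-up visit 30 days after progression with a decision not to retreat, or 30 days after retreatment stops.

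**Analysis.** Section 8.4.3 gives time to onset, time to resolution and management of high-grade select AEs by cohort, regardless of relatedness. Section 8.4.4.1 gives AE incidence by cohort. Both sections censor subjects without the event at last contact.

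**The concern.** Cohort assignment determines when dosing stops, and Section 6.1.1 ties all-cause SAE collection to that date. On its literal terms, one randomised cohort leaves all-cause collection about 14 weeks after randomisation, while the other stays in it for as long as it is dosed plus 100 days. Unrelated SAEs would then be counted over different periods in the two cohorts. For late Cohort B events, an open-label judgement of relatedness would decide whether the event is recorded at all. Both effects would make stopping treatment look safer.

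The off-drug period in Cohort B is the part of the trial that shows what happens when treatment is stopped at one year. It is also the period for which the collection rule is unclear. Serious high-grade select AEs not judged related would be among the events lost, and the secondary objective covers these whatever their cause.

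**Working it through.** **1. The plan's figure for the randomised cohorts.** Section 8.1.1 expects 99 to 322 randomised subjects. Inputs: 10 of 37 still on treatment, 780 treated. Wald interval: 0.270 ± 1.96 × √(0.270 × 0.730 / 37) = 0.127 to 0.413. Then 780 × 0.127 = 99 and 780 × 0.413 = 322, so the figure reproduces. At 1:1 that is about 50 to 161 per cohort. The documents give no length for the SAE window by cohort.

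**2. Literal end of the window, Cohort B not retreated.** (52 × 7 + 100) / 7 = 464 / 7 = week 66.3. For a stop at week 50 the result is week 64.3; for a stop at week 54 it is week 68.3.

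**3. The passages side by side, for a Cohort B subject off drug and progression-free at week 80.**

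| Source | Status at week 80 |
|---|---|
| 6.1.1 | Past 100 days from the stop; only SAEs believed related are reported |
| 3.5, 5.3.2, Table 5.1-2 | On the on-study schedule; AEs assessed continuously |
| Table 5.1-3, visit notes | Follow-up phase not yet started |
| Table 5.1-3, column heading and AE note | Counted from the last dose; beyond 100 days, only ongoing drug-related AEs followed |

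Table 5.1-3 is thus divided within itself. For a subject never retreated, its visits fall at 30 days and then about 70 days later, 100 days in total, counted from progression and the decision not to retreat. Its column heading counts the same 100 days from the last study treatment.

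**4. Possible size on the literal reading.** Time on drug after randomisation is not in the documents. Assume it is exponential in Cohort A with median 6 to 36 months, cap at 208 weeks (4 years from randomisation), and ignore death. With λ = ln 2 / median in weeks, the mean Cohort A window is (1 − exp(−λ × (208 − 14.3))) / λ + 14.3 weeks.

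| Assumed median, Cohort A | Mean window A (weeks) | B, no retreatment (weeks) | Ratio |
|---|---|---|---|
| 6 months | 51.7 | 14.3 | 3.6 |
| 12 months | 83.8 | 14.3 | 5.9 |
| 24 months | 123.3 | 14.3 | 8.6 |
| 36 months | 144.3 | 14.3 | 10.1 |

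Retreatment restarts dosing. Suppose that reopens the window, and that a share r of progressing Cohort B subjects is retreated for R weeks. The mean B window is then about 14.3 + r × (1 − exp(−λ × 208)) × (R + 14.3), with λ now for time to progression in Cohort B. With r = 0.5 to 1, R = 8 to 26 and median time to progression 6 to 24 months (all assumed), this gives 22.6 to 54.4 weeks. The top of that range matches the 51.7 weeks at the low end for Cohort A, so total length can come out about equal. The stretch from about week 66 to the start of retreatment would still be uncovered.

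**5. Whether the analysis repairs it.** Table 5.1-3 continues survival contact to five years from the start of therapy. Under last-contact censoring, a subject whose late SAE was not collected contributes event-free time up to that contact. The Kaplan-Meier estimate therefore treats uncollected time as observed. Section 8.4.4.1 summarises *on-study* SAEs without defining the term for Cohort B off drug, and neither section sets a common window or an exposure-adjusted rate.

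**The case against.** A reader might infer that all-cause SAE collection in Cohort B does stop at week 66, and that the two cohorts are therefore not comparable for safety. The documents do not establish that.

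- SAEs are AEs, and the Cohort B schedule has AEs assessed continuously until progression or later. The opening sentence of Section 6.1.1 itself asks for all SAEs after consent, related or not.
- Section 6.2.1 puts no 100-day limit on nonserious AEs, so a nonserious Grade 3 select AE is outside the rule. Section 3.6 also speaks of following select AEs beyond 100 days.
- Cohort A's window is not open-ended. It closes 100 days after its own last dose.
- The text on Cohort B's assessments after randomisation is partly redacted in the synopsis and in Sections 3.1 and 4.1. The hidden words may bear on this and cannot be held against the plan.

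Worst-case figures can also be built. A never-retreated Cohort B subject followed to five years has (260 − 66.3) / 208 = 93% of post-randomisation time outside the window. At an assumed 0.3 SAEs per person-year in both cohorts over two years, recorded incidence would be 1 − exp(−0.3 × 2) = 45% against 1 − exp(−0.3 × 100/365.25) = 8%. The latter pair requires every Cohort A subject to be under collection throughout and no Cohort B subject to be retreated. It is not an estimate for this trial.

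These points remove the claim that collection certainly stops. The conflict remains. None of the visible passages amends the cut-off in Section 6.1.1. The plan adapts vital signs, examinations, laboratory tests, thyroid tests and the first follow-up visit for Cohort B, but not the SAE window. The Section 3.6 sentence goes on to ongoing drug-related AEs, so it does not clearly cover unrelated ones. A site following Section 6.1.1 and a site following Table 5.1-2 could each believe it is compliant.

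**Conclusion.** The point holds as an unresolved conflict with a risk of differential ascertainment. It does not show that ascertainment is in fact unequal. On the literal reading, the mean all-cause SAE window after randomisation would be about 3.6 to 10 times longer in Cohort A than in Cohort B without retreatment. Retreatment narrows this and, in the most favourable assumed case, closes the difference in total length. On the schedule-based reading the windows are broadly similar. These sizes rest on assumed time on drug, time to progression and retreatment.

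The consequence is limited. At risk are the descriptive summaries by cohort, secondary in Section 8.4.3 and exploratory in Section 8.4.4.1; no test of A against B is planned in either. The events at risk are late SAEs not judged related, including serious high-grade select AEs. The primary endpoint counts treatment-related select AEs in all treated subjects and is largely protected, since related SAEs stay reportable after the window. The point should be corrected because the remedy is small and missing late events cannot be recovered by analysis.

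**What to change.** - **Section 6.1.1.** Reconcile it with Section 3.5 and Tables 5.1-2 and 5.1-3 by stating that in Cohort B all-cause AE and SAE collection continues through the on-study period, until 100 days after the last retreatment dose or after the decision not to retreat. This matches the 30 + 70 day visits already in Table 5.1-3.
- **Sections 8.4.3 and 8.4.4.1.** Summarise Cohorts A and B over an identical window from randomisation. Define *on-study* for Cohort B off drug. Censor event-free subjects at the end of AE collection, not at last contact.
- **Fallback.** If late Cohort B data prove incomplete, restrict the by-cohort summaries to the first 100 days after the week 52 randomisation in both cohorts. All-cause collection is required in both over that period on either reading. If the last Cohort B dose precedes randomisation, shorten the common window by that interval.

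The cost is a few sentences of text and some extra SAE reports from Cohort B. Those subjects are already due for clinical assessment every 2 or 4 weeks, so no new visits are needed. The fallback gives up information on later events. The change concerns data collection and analysis only.
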